5.1.1.2.2 Complementary Output

5.1.1.2.2.1 Subgroup Analysis by Race and Gender

Subgroup analyses by gender and race will be provided in Appendix 15 of the CSR.

The gender subgroup analyses will have two categories (Female and Male), and the race subgroup analyses will have four categories (White, Black, Asian, and Other).

The following subgroup analyses will be performed between Group 1 and Group 2 by gender and race.

Safety overview after any vaccine injection by gender- Overall Safety Analysis Set

Safety overview after vaccine injections at 2 months of age by gender – Safety Analysis Set 1

Safety overview after vaccine injections at 4 months of age by gender – Safety Analysis Set 2

Safety overview after vaccine injections at 6 months of age by gender – Safety Analysis Set 3

Safety overview after vaccine injections at 12 months of age by gender - Safety Analysis Set 4

Safety overview after vaccine injections by gender –Safety Analysis Set for All 4-Dose Vaccination

Safety overview after any vaccine injection by race – Overall Safety Analysis Set

Safety overview after vaccine injections at 2 months of age by race – Safety Analysis Set 1

Safety overview after vaccine injections at 4 months of age by race – Safety Analysis Set 2

Safety overview after vaccine injections at 6 months of age by race – Safety Analysis Set 3

Safety overview after vaccine injections at 12 months of age by race – Safety Analysis Set 4

Safety overview after vaccine injections by race – Safety Analysis Set for All 4-Dose Vaccination

5.1.1.2.2.2 Subgroup Analysis by Preterm and Full-term Birth

The following subgroup analyses by preterm (gestational age < 37 weeks) and full-term birth (gestational age ≥ 37 weeks) between Group 1 and Group 2 will be provided in Appendix 15 of the CSR.

Safety overview after any vaccine injection by the preterm and full-term birth – Overall Safety Analysis Set

Safety overview after vaccine injections by the preterm and full-term birth –Safety Analysis Set for All 4-Dose Vaccination

5.1.1.2.2.3 Sensitivity Analysis due to COVID-19 Pandemic

The impact of COVID-19 pandemic situation on study conduction will be summarized through impact on visit procedures, study completion and major/critical protocol deviations due to COVID-19.

The subjects impacted by COVID-19 pandemic situation will be defined as the subjects with at least one major/critical protocol deviation due to COVID-19 or who did not complete the study due to COVID-19. If more than 10% of subjects are impacted as per this definition, baseline and demographics characteristics, and main safety endpoints will also be summarized in the subsets of subjects impacted/non-impacted subjects to assess the potential impact of COVID-19 situation on study outcome.

The assessment of the impact COVID-19 pandemic will be based on but not limited to the following analysis

- To summarize the impact of COVID-19 on the overall study conduct
 - Early termination due to COVID-19
 - Impact on visit conduct (visit not done, partially done, data collection method/procedure change)
 - Major and critical protocol deviations due to COVID-19
- To summarize disposition across study visits for subjects impacted/not impacted by COVID-19
- To summarize baseline demographics by randomized group for subjects impacted /not impacted by COVID-19
- To provide an individual listing of subjects impacted by COVID-19 and how they were impacted
- To provide a listing of visits impacted by COVID-19 and how they were impacted
- To assess the potential impact of COVID-19 on the main safety endpoints in the subsets of impacted/non-impacted subjects

5.2 Analysis Sets

Six analysis sets will be used: the Overall Safety Analysis Set for any dose, Safety Analysis Set for vaccination 1 (SafAS1), Safety Analysis Set for vaccination 2 (SafAS2), Safety Analysis Set for vaccination 3 (SafAS3), Safety Analysis Set for vaccination 4 (SafAS4), and Safety Analysis Set for all 4-dose vaccinations.

5.2.1 Safety Analysis Set

The SafAS is defined as those subjects who have received at least 1 dose of the study vaccine(s)^a and have any safety data available. Specific safety analysis will be defined and used after each vaccination. Safety analysis after all 4-dose vaccinations will also be conducted as well.

All subjects will have their safety analyzed after each dose according to the vaccine they actually received, after any dose, and after all 4 doses according to the vaccine received at the first dose.

Safety data recorded for a vaccine received out of the protocol design will be excluded from the analysis (and listed separately).

_

^a A study vaccine is any vaccine that is administered as part of the study, including the investigational product (MenACYW conjugate vaccine), the control vaccine (Menveo), and the routine vaccines.

5.2.1.1 Overall Safety Analysis Set for Any Dose

The overall SafAS is defined as those subjects who have received at least one dose of the study vaccines and have any safety data available. All subjects will have their safety analyzed after any dose according to the vaccine received at the first dose.

Safety data recorded for a vaccine received out of the protocol design will be excluded from the analysis (and listed separately).

5.2.1.2 Safety Analysis Set for Vaccination at 2 Months of Age

The SafAS1 is defined as those subjects who have received the study vaccine at Visit 1 around 2 months of age and have any safety data available. All subjects will have their safety analyzed after the Visit 1 dose according to the vaccine they actually received at Visit 1.

Safety data recorded for a vaccine received out of the protocol design at Visit 1 will be excluded from the analysis (and listed separately).

5.2.1.3 Safety Analysis Set for Vaccination at 4 Months of Age

The SafAS2 is defined as those subjects who have received the study vaccine at Visit 2 around 4 months of age and have any safety data available. All subjects will have their safety analyzed after this dose according to the vaccine they actually received at that visit.

Safety data recorded for a vaccine received out of the protocol design at Visit 2 will be excluded from the analysis (and listed separately).

5.2.1.4 Safety Analysis Set for Vaccination at 6 Months of Age

The SafAS3 is defined as those subjects who have received the study vaccine at Visit 3 at around 6 months of age and have any safety data available. All subjects will have their safety analyzed after this dose according to the vaccine they actually received at this visit.

Safety data recorded for a vaccine received out of the protocol design at Visit 3 will be excluded from the analysis (and listed separately).

5.2.1.5 Safety Analysis Set for Vaccination at 12 Months of Age

The SafAS4 is defined as those subjects who have received the study vaccine at Visit 4 at around 12 months of age and have any safety data available. All subjects will have their safety analyzed after this dose according to the vaccine they actually received at that visit.

Safety data recorded for a vaccine received out of the protocol design at Visit 4 will be excluded from the analysis (and listed separately).

5.2.1.6 Safety Analysis Set for all 4-dose Vaccinations

The SafAS for all 4-dose vaccinations is defined as those subjects who have received all 4 doses of the study vaccine (3 doses in infancy and 1 dose in the second year of life at 12 months of age) and have any safety data available. All 4-dose vaccinations received in a series should be either all MenACYW conjugate vaccine or all MENVEO[®].

Safety data recorded for subjects not receiving all 4 doses of MenACYW or MENVEO® will be excluded from the analysis (and listed separately).

5.2.2 Populations Used in Analyses

The safety analysis will be performed on the Overall Safety Analysis Set for any dose, SafAS1 through SafAS4, and Safety Analysis Set for all 4-dose Vaccinations. Subjects will be analyzed according to the vaccine they actually received.

5.3 Handling of Missing Data and Outliers

5.3.1 Safety

No replacement will be done. In all subject listings, partial and missing data will be clearly indicated as missing.

5.3.1.1 Immediate

For unsolicited non-serious systemic AEs, a missing response to the "Immediate" field is assumed to have occurred after the 30-minute surveillance period and will not be imputed.

For SAEs, missing or partially missing elapsed time from last vaccination recorded if within 24 hours will be assumed to have occurred after the 30-minute surveillance period and will not be imputed. Such SAEs will not be considered as immediate.

5.3.1.2 Causality

By convention, all events reported at the injection site (either solicited or unsolicited) will be considered as related to the administered product and then referred to as reactions. In a same way, all solicited systemic events pre-listed in the CRF are also considered as related to vaccination and will be considered as reactions.

• For unsolicited systemic AE, missing relationship will be considered as related to study vaccine at the time of analysis.

The missing relationship to study procedures for SAEs will not be imputed.

5.3.1.3 Measurements

Partially missing temperatures will be handled as described in Section 4.2.1.1.1.

5.3.1.4 Intensity

For solicited reactions, missing intensities will be handled as described in Section 4.2.1.1.1. For unsolicited non-serious AEs, missing intensities will remain missing and will not be imputed.

5.3.1.5 Start Date and End Date

Missing or partially missing start dates for unsolicited AEs will remain missing and not be imputed. If either the start or stop date is missing or partially missing, the time of onset will be considered to be missing. Nevertheless, unsolicited AEs with missing time of onset will be included in analyses according to the visit collected.

Missing or partially missing stop dates for AEs (solicited reactions and unsolicited AEs) will remain missing and not be imputed.

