4.2.1.2.4 Time of Onset

Time of onset is derived from the start date of the unsolicited AE and the date of last vaccination as described in Section 4.2.1.2.3

Time of Onset = start date of the unsolicited AE – date of last vaccination before the unsolicited AE

The time of onset should be considered as missing only if one or both dates are missing or partially missing.

The unsolicited AEs will be analyzed "Within 30 days", which corresponds to AEs with a time of onset between 0 and 30 days after each vaccination or missing. An AE with missing time of onset will be considered to have occurred just after the vaccination (computed according to Section 4.2.1.2.3), so will be included in these tables. Time of onset period is displayed as D0-D3, D4-D7, D8-D14, D15 or later, and Missing.

Note: Unsolicited AEs that occurred before vaccination (negative time of onset) or with a time of onset higher than defined above will not be included in the safety analysis but will be listed.

4.2.1.2.5 **Duration**

Duration is derived from the start and end dates of the unsolicited AE: Duration = End date of unsolicited AE - start date of unsolicited AE + 1.

The duration should be considered as missing only if one or both of the start and end dates of the unsolicited AE is missing or partially missing.

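### SAP 5.3.1.5 sets time of onset to missing when only the stop date is missing, contradicting SAP 4.2.1.2.4; if programmed, it discards known onset days for unsolicited AEs

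*SAP*

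**What the plan says.** **Onset (SAP 4.2.1.2.4).** Time of onset is the AE start date minus the date of the last vaccination before it. The section adds: "The time of onset should be considered as missing only if one or both dates are missing or partially missing". The two dates meant are the start date and the vaccination date.

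**Use of onset (same section).** The within-30-days analysis takes in unsolicited AEs by a rule "which corresponds to AEs with a time of onset between 0 and 30 days after each vaccination or missing". It explains that "An AE with missing time of onset will be considered to have occurred just after the vaccination". The display rule is: "Time of onset period is displayed as D0-D3, D4-D7, D8-D14, D15 or later, and Missing". Events "with a time of onset higher than defined above will not be included in the safety analysis but will be listed".

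**Duration (SAP 4.2.1.2.5).** This is where the end date enters: "The duration should be considered as missing only if one or both of the start and end dates" are incomplete.

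**Missing data (SAP 5.3.1.5).** Here the rule is different: "If either the start or stop date is missing or partially missing, the time of onset will be considered to be missing". The section continues that "unsolicited AEs with missing time of onset will be included in analyses according to the visit collected", and it leaves missing stop dates unimputed.

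**Why stop dates may be missing.** Footnotes in Protocol 9.1.1.3.3 and SAP 4.1.1.3.3 have stop dates actively sought only for related AEs. An AE with no stop date is treated as still ongoing when the study ends.

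**The concern.** A stop date carries no information about when an event began. Making onset depend on it discards a day count that can be calculated from two complete dates. Because 4.2.1.2.4 admits events with missing onset to the 30-day tables, the rule in 5.3.1.5 could also change which events are counted there.

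Safety description is the trial's only objective. For unsolicited non-serious AEs, SAP Table 5.2 reports both the D0-D30 percentage of subjects and the time of onset. Two programmers, each following a current section of the same SAP, could produce different versions of these outputs.

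**Working it through.** The plan states no figure to reproduce. The check applies each rule to the same events and compares where they land.

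**Inputs**
- Rule A (SAP 4.2.1.2.4): onset = start date − last vaccination date; missing only if one of these is incomplete.
- Rule B (SAP 5.3.1.5): onset is also missing if the stop date is incomplete.
- Window (SAP 4.2.1.2.4): counted as within 30 days if 0 ≤ onset ≤ 30 or onset is missing; listed only if onset > 30.
- Dose (SAP 4.2.1.2.3): a complete start date that is not a vaccination date identifies the last vaccination by itself, so no stop date is needed.

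**Step 1: stop date present.** Rules A and B agree for every start day.

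**Step 2: complete start date, no stop date.** Put the vaccination at day 0, so that onset under Rule A is simply the start day. The start days are chosen for illustration.

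| Start | Rule A | Rule B |
|---|---|---|
| D5 | onset 5, row D4-D7, in table | onset missing, row Missing, in table |
| D10 | onset 10, row D8-D14, in table | onset missing, row Missing, in table |
| D20 | onset 20, row D15 or later, in table | onset missing, row Missing, in table |
| D31 | 31 > 30, listed only | onset missing, counted within 30 days |
| D45 | 45 > 30, listed only | onset missing, counted within 30 days |

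**Step 3: starts in D0-D30.** The event remains in the D0-D30 table under either rule. The percentage of subjects, MedDRA terms, intensity, relationship and action taken do not change. Only the onset row is lost.

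**Step 4: starts after D30.** This effect requires the event to be recorded at all. For non-serious unsolicited AEs the documents conflict. Protocol 5.1.1 and SAP 3.1 collect them up to the next study visit. The Protocol Table of Study Procedures, SAP Table 3.3, Protocol 9.1.1.3.3 and SAP 4.1.1.3.3 stop at D30. On the D30 reading, essentially only Step 3 remains. On the next-visit reading, Step 4 can add events to the 30-day table. It changes the percentage of subjects with any event only for a subject who has no other qualifying event in that window.

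**Step 5: does the visit rule in 5.3.1.5 repair this?** No. Under SAP 4.2.1.2.3 the visit field identifies the dose. It cannot restore the onset day or show that a start fell after D30.

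**Step 6: number of events.** This would need the rate of missing stop dates and, for Step 4, the rate of non-serious AEs recorded after D30. The documents give neither, so no count or percentage follows.

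**The case against.** The strongest reply is that 4.2.1.2.4 is the dedicated derivation and is explicit, so the wording in 5.3.1.5 looks like a drafting slip carried over from the duration rule. SAP 5.3.1.3 and 5.3.1.4 send the reader back to section 4.2 for derivations. If 4.2.1.2.4 is programmed, nothing is misplaced. That is true, but the SAP states no order of precedence, and 4.2.1.5.4 points the other way, to 5.3.1.2, for missing causality. A programmer who follows the missing-data section is therefore not acting unreasonably.

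A second reply is that an event with no stop date has a status, ongoing, and so is not missing data. Read that way, the effect shrinks. But 5.3.1.5 does not exempt ongoing events.

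A third reply is that any effect is visible, since affected events would appear in a displayed Missing row, and that the output is descriptive. This stands and limits the weight of the point.

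A reader might also infer more than the documents support:
- **Events starting before vaccination are pulled in.** With a complete start date, 4.2.1.2.3 attaches the event to the last vaccination before it. An event before a later dose belongs to the previous dose and has positive onset. An event before the first dose has no dose table to enter.
- **SAE and MAAE windows are inflated.** SAP 4.2.1.2 does count SAEs as unsolicited AEs. But 4.2.1.3 and 4.2.1.4 set their own periods, including the whole study, without repeating the missing-onset rule. The exclusion of later events in 4.2.1.2.4 would conflict with those periods. SAP 4.1.1.3.5 records MAAEs as unsolicited AEs only to D30.
- **The days between D30 and the next visit measure the inflation.** Calendar time without an event rate or a missing-stop-date rate does not measure misplaced events.

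**Conclusion.** The contradiction is explicit, and nothing in either document resolves it. Its consequences are conditional:

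1. If 5.3.1.5 is programmed and ongoing events are treated as having a missing stop date, unsolicited AEs with a known start in D0-D30 and no stop date lose their onset row. They stay in the D0-D30 table.
2. If, in addition, non-serious AEs starting after D30 are recorded, those with no stop date are counted as within 30 days instead of only listed.

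The number of affected events cannot be derived. No hypotheses are tested, the rule is the same in both groups, and no bias between groups is shown. Whole-study tables are unaffected. Confidence is high in the contradiction and lower in the second consequence, which depends on an unresolved collection period. The point is minor.

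**What to change.** In SAP 5.3.1.5, replace the conflicting sentence with: *Time of onset is missing only if the start date or the last vaccination date is missing or partially missing; a missing stop date affects duration only.* Keep the existing convention for missing or partial start dates, including assignment by visit.

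Then check the derivation with test records that have a complete start date and no stop date, one starting inside D0-D30 and one after D30. The first should keep its onset row and the second should be listed only.

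The cost is one SAP sentence and one programming check. No new data are needed.

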5.3.1.6 Action Taken

Missing actions taken will remain missing and not be imputed.

5.3.2 Immunogenicity

Not applicable

5.3.3 Efficacy

Not applicable

5.4 Interim / Preliminary Analysis

No interim or preliminary analyses are planned.

5.5 Determination of Sample Size and Power Calculation

The sample size of this study was chosen to provide safety data; it is not intended for the purposes of hypothesis testing. No formal sample size calculation is performed.

Though there are no statistically powered hypotheses, the overall study cohort of 3080 subjects will provide a probability of approximately 95% of observing any AE with a true incidence of 0.15%. In the treatment arm with 2310 subjects, there is a probability of approximately 95% of observing any AE with a true incidence of 0.2%.

5.6 Data Review for Statistical Purposes

Reviews of the data are anticipated through the data review process led by Data Management before database lock. This review of the data will include a statistical review.

In addition, an internal Safety Management Team (SMT) will review the data being generated from all the ongoing studies with MenACYW conjugate vaccine at regular intervals for any new safety signals or safety concerns.

